An academic from UCLan, who is an expert in the use of statistics, will oversee the randomisation process. The total number of patients (n=300; IG=150, CG=150) will be randomised with a 1:1 ratio using permuted block randomisation. The groups will have equal sizes and will tend to be uniformly distributed by key-outcome-related characteristics [18].

Unit of randomisation and intervention

The patient is the unit of randomisation and intervention.

Block size

Blocked randomisation will provide a balance between study arms, reducing the opportunity for bias and confounding. The block size in this study will be two and four [19].

Sequence generation

The sequence generation will be conducted using randomisation with block permutation without stratification.

The block permutation, randomisation, and sequence generation will be performed using PASS (Power Analysis and Sample Size Software) 2021, (NCSS, LLC. Kaysville, Utah, USA, ncss.com/software/pass).

Allocation concealment

The procedure adopted in this study for assuring the allocation concealment will be the use of sequentially numbered, opaque, and sealed envelopes (SNOSE).

Blinding

In our study, the clinicians (opticians) performing the assessment and follow-up and the patients receiving and wearing the spectacles will be blinded to the treatment.

Data collection

Clinicians will collect data at baseline and 4-week intervals using paper questionnaires.

Data management

Data will be managed following the procedure used in a previous study [20]. Input data will be saved and stored on a password-protected system. Only individuals authorised by the CI will be allowed to access the data. Paper data, such as clinicians' informed consent, will be kept in a locked cabinet by the research team. Patients' informed consent will be kept by the clinicians in a locked cabinet.

Statistical methods

The primary analysis will be the intention-to-treat (ITT), including all randomised participants in the group where they were randomly assigned, regardless of their adherence to the protocol or their withdrawal.

Missing data will be assessed and treated using multiple imputation of missing at random (MAR).

To check for normality, each variable will be analysed using the Kolmogorov-Smirnov and Shapiro Wilk tests.

Primary outcome

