The primary outcome measure (CVS-Q score) will be assessed at week 14 using an unpaired analysis. The analysis will be performed without adjustments; then, it will be adjusted using the baseline CVS-Q scores, age, and gender and the CVS-Q at 6 and 10 weeks using generalized estimating equations (GEE), which is a semiparametric technique useful for repeated measures that work for dichotomous and continuous data, as in our case.

Secondary outcomes

The secondary outcome measure, the improvement of the near visual performance when using digital devices using SESL01 compared with standard single vision lenses will be assessed using the clinical measurement of accommodative facility in cycles per minute using spherical lens flippers at week 14 as well as optometric tests such as near LogMAR visual acuity, amplitude of accommodation, near point of convergence and rate of reading.

Secondary analysis

The secondary analyses will be performed looking at

- the percentage of CVS-Q score <6 (no symptoms) versus CVS-Q score ≥6 (symptoms) in each group at 14 weeks. The results will be presented using descriptive statistics at each time point, and the differences will be assessed using Pearson's Chi-square test or Fisher's exact test and odds ratio (OR).

- The percentage of participants in each group with a total CVS-Q score <6, 6-12, 13-19, and ≥ 20 at week 14. The results will be presented using descriptive statistics at each time point, and the differences will be assessed using the Mann Whitney U test.

A P-value of ≤ 0.05 will be considered statistically significant and presented with 95% confidence interval where appropriate. The statistical analysis will be performed using SPSS (IBM Corp. Released 2021. IBM SPSS Statistics for Windows, Version 28.0. Armonk, NY: IBM Corp).

Data monitoring

This trial was designed to minimise the risk, as demonstrated in a previous trial [20]. Therefore, no formal committee has been organised, and no interim analysis of the impact of the intervention has been planned. The study is a monocentric study conducted at the UCLan campus in Preston.

Risk and safety issues

During this study, there will be no risks for patients. Patients wearing the SESL01 lenses will be at no greater risk than those receiving the usual ones. Clinicians will not dispense or administer any medications based on the CVS-Q score. In addition, clinicians will not be involved in the interpretation of diagnostic tests or their results.

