Should symptoms of non-tolerance remain after the retest for the prescription and re-dispense, the information will be reported to Carl Zeiss Vision International GmbH c/o Carl Zeiss Vision UK Ltd as an adverse effect within 3 working days. Carl Zeiss Vision International GmbH c/o Carl Zeiss Vision UK Ltd has an adverse effect reporting template that will be filled in and sent to the relevant department within the lens manufacturer. Carl Zeiss Vision International GmbH c/o Carl Zeiss Vision UK Ltd will inform MHRA about any adverse effects.

Auditing

No audit has been planned at this time.

Research and dissemination

The study protocol and outcomes will be published in peer-review journals, conference papers and may be used in training materials for clinicians working in the optical industry.

Participants will be offered a copy of the final study report submitted to Carl Zeiss Vision International GmbH c/o Carl Zeiss Vision UK Ltd.

Regulatory approvals

Ethics approval will be sought from and NHS REC, and from the UCLan University REC. A notice of no objection will be sought from the MHRA.

Protocol amendments

We are not expecting to make any changes to the eligibility criteria, outcomes, and analyses during our study. Any amendments made to the protocol will be submitted to the MHRA and/or REC as appropriate.

Consent, invitation, and confidentiality

Consent will be obtained according to the International Standards Organisation (ISO) 14155 – Clinical investigation of medical devices for human subjects – Good clinical practice guidelines. The Chief Investigator (CI) or other qualified member of the study team will make the decision as to whether the potential participant is suitable for screening and/or enrolment into the study. The potential participant will then be given the patient information leaflet and consent form and will have a discussion with the study team member.

The potential participant will then be given time to consider taking part and take the opportunity to discuss the study with others such as friends and family or members of their medical team, as applicable and appropriate. Once the potential participant is satisfied that they have been fully informed, and they have decided that they wish to enter the study, they will be asked by the study team member to sign a consent form.

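### Blocks of two and four, printed in the protocol for one unstratified list of 300, make allocations highly predictable to anyone who learns earlier ones

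*Combined protocol and SAP*

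**What the plan says.** The Randomisation section states that 300 patients, 150 per arm, "will be randomised with a 1:1 ratio using permuted block randomisation". The Block size section adds "The block size in this study will be two and four". It cites a paper whose title concerns randomly selected block sizes, but the protocol does not itself say that the order of the sizes is random or withheld. Sequence generation is by "randomisation with block permutation without stratification", and the Data monitoring section confirms one centre: "The study is a monocentric study conducted at the UCLan campus in Preston". There is therefore one allocation list.

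Concealment is by numbered, opaque, sealed envelopes. The Blinding section covers patients and the opticians who assess and follow them up. It does not mention whoever opens the envelopes, orders the lenses or dispenses them. The Clinician-patient ratio section gives 300:1 for frame selection and measurements, which implies that one person sees every participant.

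The Research and dissemination section says that the protocol will be published, without saying when.

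**The concern.** Small blocks are useful when a list is split over many strata or small centres, because each short list must balance by itself. Neither applies here. Two is the smallest possible block at 1:1, and its second allocation is fixed by its first.

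Printing the sizes gives anyone who also sees allocations the means to anticipate the next one. Two things are at stake. First, under the Consent section a study team member judges suitability, and entry depends on a self-reported CVS-Q score of at least 6. Foreknowledge could influence who is enrolled, and when. Second, the primary outcome is also the self-reported CVS-Q, so the comparison leans heavily on the double-blind claim.

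**Working it through.** The plan states no predictability figure, so there is nothing of its own to reproduce.

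**Inputs from the protocol:** block sizes 2 and 4, ratio 1:1, N = 300, no strata, one site.

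**Assumption:** a proportion p of the blocks has size two. The central value is p = 0.5, with range 0.25 to 0.75. The mean block length is L = 2p + 4(1 − p), which is 3.0 at p = 0.5, 3.5 at p = 0.25 and 2.5 at p = 0.75.

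**1. Earlier allocations and block boundaries known.** In a block of 2m, the expected fraction of certain allocations is 1/(m + 1). A block of two has 1 of 2. A block of four has 4/3 of 4: the fourth always, and the third when the first two are alike (probability 1/3). The overall fraction is [p + (4/3)(1 − p)]/L.
- p = 0.5: (0.5 + 0.667)/3 = 7/18 = 38.9%, about 117 of 300
- p = 0.25: 1.25/3.5 = 35.7%
- p = 0.75: 1.083/2.5 = 43.3%

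**2. Earlier allocations known, order of sizes unknown.** Certainty arises only when the first two of a block of four are alike (probability 1/3). The running difference of two then shows that the block has size four, and both remaining places are forced. That is 2/3 of an allocation per block of four, so the fraction is (2/3)(1 − p)/L.
- p = 0.5: 0.333/3 = 11.1%
- p = 0.25: 0.5/3.5 = 14.3%
- p = 0.75: 0.167/2.5 = 6.7%

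Simulated lists gave 10.8%, 14.1% and 6.8%.

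**3. Best guess.** The observer guesses whichever arm is behind. The expected number correct in a block of 2m is m + 2^(2m−1)/C(2m, m) − 1/2.
- Block of two: 1 + 1 − 0.5 = 1.5 of 2
- Block of four: 2 + 8/6 − 0.5 = 2.833 of 4
- Equal mix: (1.5 + 2.833)/6 = 72.2%, against 50% by chance

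Every block ends in balance, so this rule needs only the running difference and not the boundaries. Simulation gave 72.2% with boundaries known and 72.1% without.

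**4. One member of a consecutive pair unmasked.** Both sizes are even, so patients 1–2, 3–4 and so on always share a block. The other member is in the opposite arm with probability 1 in a block of two and 2/3 in a block of four. A block of four holds two such pairs.
- p = 0.5: (1 + 2 × 2/3)/3 = 7/9 = 77.8%
- p = 0.25: 1.25/1.75 = 71.4%
- p = 0.75: 1.083/1.25 = 86.7%

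**5. No earlier allocation known.** The next allocation is 50:50, and none is certain.

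**6. Comparison: sizes 6, 8 and 10 in equal proportions.**
- Certain with boundaries known: (1.5 + 1.6 + 1.667)/24 = 19.9%, about 60 of 300
- Best guess: (4.1 + 5.329 + 6.532)/24 = 66.5%

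**The case against.** The strongest reply is that block size by itself discloses nothing. Envelopes are opaque, and patients and assessing opticians are blinded. If that holds, step 5 applies. This stands, and every figure above depends on a leak.

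The 39% also needs knowledge of every block boundary. The cited paper suggests a random order of sizes, which would bring certain allocations down to about 11%. That is fair, although the plan does not state it, and the 72% guess rate does not depend on it.

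Three stronger readings are tempting, and the documents do not support them.

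- A reader might infer that unmasking one patient always reveals the neighbour. That is certain only in a block of two.
- A reader might infer that non-tolerance cases, of which the Harm section expects about seven, will expose the lens design. The text mentions only a "retest for the prescription and re-dispense". It does not say that the design is recognised there, and Figure 2, which sets out the process, is not available in the text reviewed. Some cases concern frame fit or measurements. With one third of patients in blocks of two (2/6 at an equal mix), seven unmaskings would settle about 7 × 1/3 ≈ 2 neighbours. These cases also cannot arise before spectacles are collected at week 2. A June to September study (about 17 weeks) with 14 weeks of follow-up leaves about 3 weeks to enrol, so the neighbour would almost always be randomised already. Staff who infer a neighbour's arm do not thereby unblind that patient.
- A reader might infer that larger blocks remove most of the predictability. They roughly halve the certain allocations, but 16.5 of the 22.2 points of guessing above chance (74%) remain.

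**Conclusion.** The point holds in conditional form. Nothing in the plan is contradictory or miscalculated, and no bias is shown. Once earlier allocations are known, blocks of two and four leave between about one in nine (order unknown) and about two in five (boundaries known) of the remaining allocations certain, and about 72% correctly guessable. These figures rest on an assumed equal mix of sizes; the ranges in the working cover 25% to 75% of blocks being of size two.

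A leak is possible because someone must open envelopes and order lenses, and the plan does not name that person as blinded. No stratum or small centre calls for a block of two. This is an inexpensive improvement, not a condition for the trial to be valid.

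**What to change.** Before the first envelope is prepared, regenerate the list without blocks of two, using larger randomly varied blocks such as 6, 8 and 10. In the protocol, say only that permuted blocks of varying size are used. Keep the sizes in a restricted randomisation document that recruiting and dispensing staff do not see. Withholding the sizes matters as much as enlarging them: with all earlier allocations known but the order of sizes unknown, simulated mixes of 4, 6 and 8 and of 6 and 8 left only about 2% and 4% of allocations certain. State also who holds the list, who opens the envelopes and orders the lenses, and whether they have any part in enrolment or assessment.

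The cost is one regenerated list and a slightly looser final balance. The largest possible imbalance is half the largest block: 10/2 = 5 instead of 4/2 = 2. If recruitment stops at exactly 300 it is at most 4, because all block sizes are even. Exactly 150 per arm is then not guaranteed. The effect on power is negligible: efficiency relative to equal arms is 1 − (5/300)² = 0.9997.

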- VIII. Change in ± 0.75 DS/DC in the spectacle prescription [15-20].

Intervention

Participants in the intervention group will wear the newly designed SESL01 lens. The SESL01 is an Enhanced Single Vision Lens design. Enhanced Single Vision Lenses (ESL) have a small amount of positive power towards the bottom of the lens, as this is the area that is in line with the eye when looking downwards for near tasks. The small amount of positive power is expected to reduce the effort by the eyes to maintain a clear, in-focus image when looking at tasks at near.

Patients in the control group will be corrected with standard single vision lenses with an anti-reflection coating.

[figure not shown]
Both patient groups will have a choice of spectacle frames (within a set price range of up to £70) to select for their new spectacle correction. At the end of the study, all spectacles will be returned to the research team so that they can be reglazed with standard single vision lenses with an anti-reflection coating ensuring that the intervention lens (SESL01) is not in the public domain ahead of its official release.

Table 1 Schedule of enrolment, intervention, and assessments

	Study period					
	Enrolment Screening	Allocation Baseline	Spectacle collection	Post-allocation		Closeout
Timepoint (weeks)	-W0	W0	W2	W6	W10	W14
Enrolment						
Eligibility screen for patients	x					
Informed consent for patients		x				
Randomisation for patients		x				
Spectacles collection			x			
Intervention Group will use the Super Enhanced Single Vision Lens L01 (SESL01)			x	x	x	x
Control Group will use the standard single vision lenses			x	x	x	x
Assessments						
Computer Vision Syndrome Questionnaire (CVS-Q)	x	x		x	x	x
LogMAR Vision and Visual Acuity (using a computerised chart: 6/6 minimum monocular distance VA and N6 monocular)		x		x	x	x
Non-cycloplegic refractive error assessment (anisometropia of ≤ 1.50 DS in any one meridian, +4.00 to 6.00DS and +2.00DC)		x				
Cover test (D&N)		x				
Ocular Motility		x				
Pupil size (D&N)		x				
Fixation Disparity (D&N)		x				
Monocular and binocular amplitude of accommodation		x		x	x	x
Near point of convergence		x		x	x	x
Slit lamp Assessment (including measuring of tear break-up time, less than 11sec is an exclusion criteria)		x				
Indirect assessment of the fundus (Volk)		x				
Optical Coherence Tomography imaging		x				
Intra-Ocular Pressure measurements for those aged 40yrs and over		x				
Visual Fields		x				

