Seguí-Crespo et al. [20] and Alhasan et al. [24] suggested that the CVS-Q score is not normally distributed. Alghamdi and Alrasheed [23] and Sanchez Brau et al. [25] summarised their findings using means and a wide range of standard. Therefore, in our study it was decided to conduct the power calculation using a standard deviation of 3.5, which is within the 1.8-6 range. We also assumed an initial normal distribution in the arms with expected means of 8 in the control and 6 in experimental groups. We then estimated the power for different sample sizes by simulation, truncating the values generated to select those at least 6. The result was that a sample size of 150 per group would give us a power of 80% to detect the clinically important difference of 2, even allowing for a dropout of 10%. Therefore, with a 1:1 allocation and sample size of 300 patients (150 in the intervention group [IG] and 150 in the control group [CG]), we expect there to be sufficient power to detect this effect size.

Recruitment

Recruitment will be focussed mainly on students and staff within the University of Central Lancashire.

Student recruitment: Announcements on the virtual learning platform (the Blackboard) will be used along with posters around the campus with the details of the study. Project invites can be sent out via Social Media accounts and student email addresses. The university has a large portion of mature students, so recruiting patients within the required age range will be possible.

Staff recruitment: Emails, announcements on internal comms, social media accounts, work email addresses, and posters will be used to encourage colleagues to participate.

Recruitment will start as soon as University ethics and NHS REC approval have been granted and the sponsor has opened the study site.

The recruitment strategy will increase potential participants' awareness of the health problem being studied, its potential impact on their health, and engagement in the learning and training of healthcare professionals.

Clinician-patient ratio

For eye test and clinical measurements, the ratio of participants to clinicians is 150:1 but each interaction/data collection appointment will be on a 1:1 basis.

For spectacle frame selection and measurements, the ratio is 300:1; however, each interaction will be on a 1:1 basis.

Randomisation, sequence generation, allocation, and blinding

Randomisation

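### The screening CVS-Q score is not named as a covariate; adding it could modestly improve the precision of the adjusted week-14 comparison

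*Combined protocol and SAP*

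**What the plan says.** In Table 1 of the combined protocol and SAP, the row beginning "Computer Vision Syndrome Questionnaire (CVS-Q" is marked at screening (-W0), W0, W6, W10 and W14. Eligibility screening sits in the first of these columns. Consent and randomisation sit at W0, the column labelled as baseline, and spectacles are collected at W2.

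Under Statistical methods, Primary outcome, the week-14 score is first compared between arms without adjustment. In the second step, "it will be adjusted using the baseline CVS-Q scores, age, and gender"; the CVS-Q at weeks 6 and 10 also enters, through GEE. The screening score is not mentioned. The plan calls for multiple imputation but does not list the variables in the imputation model.

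The Sample size section supplies the scale: "a sample size of 150 per group would give us a power of 80% to detect the clinically important difference of 2", "using a standard deviation of 3.5, which is within the 1.8-6 range" and "expected means of 8 in the control and 6 in experimental groups".

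**The concern.** One CVS-Q reading is an imperfect measure of a person's usual symptom level. Two readings taken before the lenses are worn can predict the week-14 score better than one, and the residual variance of the adjusted model falls accordingly. The second reading is already scheduled. If it is left out, the adjusted arm effect may be somewhat less precise than the collected data allow.

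There is also a point of definition. With two pre-treatment scores and the plural, undefined term for baseline scores, an analyst could use either one. If the entry rule is applied at screening, the screening score is selected to be high and will tend to exceed the W0 score through regression to the mean. The two are therefore not interchangeable.

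**Working it through.** **Inputs from the documents.** SD 3.5; means 8 and 6; 150 per arm; 10% dropout, leaving 135 per arm; entry at a CVS-Q of 6 or more; significance rule "A P-value of ≤ 0.05 will be considered statistically significant" (two-sided assumed).

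**Inputs assumed.** The documents give no correlation between CVS-Q occasions and no interval from screening to W0. Let r be the correlation of each pre-treatment score with week 14 (0.3 to 0.7), and s the correlation between screening and W0 (from r up to 0.95).

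**The plan's own figure.** The stated power is 80%, obtained by "truncating the values generated to select those at least 6" and "even allowing for a dropout of 10" per cent. Truncating at 6 and resampling to full size gives means 9.66 and 8.79 (difference 0.863) and SDs 2.489 and 2.110. At 135 per arm, SE = √[(2.489² + 2.110²)/135] = 0.281, and power = Φ(0.863/0.281 − 1.96) = 86.8% by t-test. Mann-Whitney simulation gives about 83 to 84%. The 80% is not reproduced exactly, but these results fit a claim of at least 80%. They are used here only for scale.

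**Variance formulas, as multiples of the pre-selection variance.**
- No selection: W0 alone leaves 1 − r². Both scores leave B = 1 − 2r²/(1 + s).
- Selection at screening, pre-selection mean 8: the screening variance shrinks to k = (2.489/3.5)² = 0.506 of its value. Put d = 1 − k = 0.494. W0 alone then leaves A = (1 − r²d) − (r − rsd)²/(1 − s²d). Both scores still leave B.

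Example, r = s = 0.5: A = 0.876 − 0.376²/0.876 = 0.715 and B = 0.667, so the cut is 1 − 0.667/0.715 = 6.7%.

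| r | s | A (W0 only) | B (both) | Cut, selected at screening | Cut, no selection |
|---|---|---|---|---|---|
| 0.3 | 0.3 | 0.887 | 0.862 | 2.9% | 5.3% |
| 0.5 | 0.5 | 0.715 | 0.667 | 6.7% | 11.1% |
| 0.7 | 0.7 | 0.481 | 0.424 | 12.0% | 17.0% |
| 0.5 | 0.8 | 0.743 | 0.722 | 2.8% | 3.7% |
| 0.7 | 0.8 | 0.496 | 0.456 | 8.1% | 10.7% |
| 0.5 | 0.9 | 0.748 | 0.737 | 1.5% | 1.8% |
| 0.7 | 0.9 | 0.506 | 0.484 | 4.3% | 5.1% |

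The first three rows are the favourable case, because they make screening and W0 no more alike than W0 and week 14. The last four make the closer pair more alike, which is more plausible. At r = s = 0.7, a pre-selection mean of 6 or 10 instead of 8 gives about 10% or 14%.

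**Correlation that decays with time.** If the screening-to-week-14 correlation equals r × s (first-order autoregression), the screening score adds 0%. That result requires W0 to be free of measurement error. Suppose instead reliability 0.7 to 0.9, true screening-W0 correlation 0.90 to 0.95 and true W0-week-14 correlation 0.75. The three observed correlations are then reliability times the matching true value, and the cut is about 1.5 to 3.7% with selection at screening.

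**Weeks 6 and 10 as covariates.** With p equally correlated scores and no selection, the residual factor is 1 − pr²/[1 + (p − 1)r]. Going from p = 3 (W0, W6, W10) to p = 4 gives 0.625 to 0.600 at r = 0.5 (4%) and 0.3875 to 0.368 at r = 0.7 (5%).

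**Practical scale.** At r = s = 0.5 with 150 per arm, SE = 3.5 × √(0.715 × 2/150) = 0.342 with W0 alone and 0.330 with both. The 95% half-width goes from 0.67 to 0.65 points, against a target difference of 2. In the truncated scenario at 135 per arm, power is Φ(3.07/√f − 1.96), where f is the residual variance relative to the selected variance. Simulated f gives 89.1% to 89.9% at r = s = 0.3 (f 0.929, 0.902), 92.5% to 94.1% at 0.5 (f 0.817, 0.763) and 97.1% to 98.4% at 0.7 (f 0.636, 0.559). Without truncation, power is 99.7% before any adjustment.

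**The case against.** The strongest reply is that the plan already adjusts for baseline, and that leaving out a second and perhaps nearly identical reading is ordinary practice. Most of this stands.

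- **Interval.** None is stated. The consent section describes the eye test as the screening assessment, yet Table 1 puts the eye-test items at W0, and the Data collection section mentions only baseline and 4-week intervals. That is compatible with one visit. Against this, the same consent section allows thinking time between the suitability decision and consent, and Table 1 puts consent at W0, which suggests a gap. The documents do not settle it.
- **Scope.** Only the adjusted analysis changes, and the plan does not say whether the adjusted or the unadjusted comparison is decisive.
- **Model.** The main calculation is an ANCOVA on W0, not the GEE described. With weeks 6 and 10 as covariates the gain is 4 to 5% in the case computed. With them as repeated outcomes it depends on the estimand.
- **Availability.** Table 1 places the screening CVS-Q before consent, while the consent section rules out study-specific measures until consent is signed.

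A reader might infer that the plan throws away a free covariate that would certainly cut the variance of the primary effect by 7 to 12%, or by 11 to 17% without selection. The documents do not support that. Those figures need the favourable correlation pattern, they do not touch the unadjusted analysis, and it is not established that a usable, consented score on an earlier day exists for everyone. It is also not explicit that only the W0 score is meant.

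What survives the objection is that two pre-treatment scores are scheduled, that baseline is undefined, and that naming both scores costs almost nothing.

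**Conclusion.** The point holds in a small, conditional form. Adding the screening CVS-Q to the adjusted model could lower the variance of the week-14 arm effect by about 0 to 12% when entry is judged on the screening score (pre-selection mean 8). About 2 to 8% is most plausible, for r of 0.5 to 0.7 and s of 0.8 to 0.9. The gain is near zero if the forms are completed together. If the entry rule were applied to the W0 score instead, the no-selection column would apply under normality, because conditioning on W0 removes the effect of that selection.

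All of this rests on assumed correlations. In the equal-correlation cases computed, the power gained beyond W0 adjustment is about 1 to 1.6 points, so no conclusion of the trial is at risk. It is a worthwhile optional improvement, not a defect. Which comparison is decisive, and how weeks 6 and 10 enter the GEE, are separate questions that matter more.

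**What to change.** In the primary outcome paragraph under Statistical methods, define baseline CVS-Q as the W0 score. State that the adjusted model and the imputation model also include the screening CVS-Q as a separate continuous covariate, where it was taken on an earlier occasion and consent covers its use. Before relying on it, reconcile the timing of the screening CVS-Q and of consent in Table 1 with the consent section, and state the interval from screening to W0.

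The cost is one sentence in the plan and one degree of freedom among about 270 completers (300 less 10%). No extra data collection is needed.

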The following formula will be used to calculate the total score

$$\text{Score} = \sum_{i=1}^{16} (\text{frequency of symptom occurrence})_i \times (\text{intensity of symptom})_i$$

Seguí et al. [17] suggested that a good balance between sensitivity and specificity is represented by a cut-off value of 6 for the total CVS-Q score. Therefore, patients with a CVS-Q total score ≥ 6 are suffering from CVS and will be included in the study. In the absence of a universal consensus on CVS severity grading, Alhasan et al. [24] adopted the following criteria: participants with a total score of 6-12 were deemed to have mild CVS, those with a score of 13-19 moderate, and those with a score ≥ 20 were considered to have severe CVS.

Outcomes

Primary outcome

The primary outcome measure is the effectiveness of the SESL01 in reducing the CVS compared with standard single vision lenses, assessed using the CVS-Q® scores at week 14.

Secondary outcome

The secondary outcome is the effectiveness of SESL01 compared with standard single vision lenses in improving the near visual performance when using digital devices assessed by clinical measurement of accommodative facility in cycles per minute using spherical lens flippers as well as optometric tests such as near LogMAR visual acuity, amplitude of accommodation, near point of convergence and rate of reading.

In addition to performance of the lens in terms of reducing CVS and improving near vision function, the study will consider the safety of the lens before it can be prescribed safely to the wider population.

Sample size

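### The adjusted primary model can be read two ways, one of which conditions on post-treatment CVS-Q, and the plan does not say which analysis decides

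*Combined protocol and SAP*

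**What the plan says.** Under Outcomes, the primary outcome is the comparison of the arms "assessed using the CVS-Q® scores at week 14". Under Statistical methods, Primary outcome, week-14 CVS-Q is to be compared by an unpaired analysis, with no test named. Two analyses follow in sequence: "The analysis will be performed without adjustments; then, it will be adjusted". The adjustment is described as "adjusted using the baseline CVS-Q scores, age, and gender and the CVS-Q at 6 and 10 weeks using generalized estimating equations". GEE is then justified as a method "which is a semiparametric technique useful for repeated measures that work for dichotomous and continuous data".

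No model is written out. The plan gives no arm-by-visit term, no week-14 contrast and no working correlation.

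The only statement about what is primary is in the opening of Statistical methods: "The primary analysis will be the intention-to-treat (ITT), including all randomised participants in the group where they were randomly assigned". That fixes the population and not the model. One threshold serves every analysis: "A P-value of ≤ 0.05 will be considered statistically significant". In Table 1 the row "Spectacles collection" is marked at W2, and CVS-Q is assessed at W6, W10 and W14 after baseline.

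**The concern.** The sentence supports two models that estimate different quantities.

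- **Covariate reading (the grammar).** CVS-Q at weeks 6 and 10 stands in the same list as baseline CVS-Q, age and gender. Those visits fall 4 and 8 weeks after lens wear can start, so the scores are themselves affected by treatment. The arm coefficient then measures only the part of the week-14 difference that the earlier scores do not already carry.
- **Response reading (the stated reason for GEE).** Weeks 6, 10 and 14 are all outcomes, and nothing is removed by conditioning. But if the model has no arm-by-visit term, its single arm coefficient is an average over the three visits. It equals the week-14 effect only when the effect is constant.

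This is the only planned analysis that uses baseline CVS-Q. If it disagrees with the unadjusted comparison, the plan has no rule for which result stands. The model and the decisive result could then be chosen after the data are seen.

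**Working it through.** **Inputs from the documents (Sample size; Statistical methods).** 150 per arm, 10% dropout, so 150 × 0.9 = 135 per arm; target difference 2 points; SD 3.5, from a cited range of 1.8 to 6; threshold 0.05, taken as two-sided because the plan does not say.

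**Inputs not in the documents (assumptions).** Between-visit correlation ρ of 0.5 to 0.7, either exchangeable or AR(1) by visit. Effect at weeks 6, 10 and 14, as points of reduction: constant (2, 2, 2), building (1, 1.5, 2), or week 14 only (0, 0, 2).

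**The plan's own power figure.** The stated power is 80% for a difference of 2, from a simulation truncated at scores of at least 6. Untruncated, 135 per arm at SD 3.5 gives 99.7%. Truncated and redrawn to 135 per arm, it is 87% (t-test) or 83% (Mann-Whitney). The 80% is not reproduced exactly, because the test and the truncation procedure are not described. The present point does not depend on it. The powers below are untruncated and should not be set against the 80%.

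**Covariate reading, estimate.** Regress week 14 on arm, baseline, week 6 and week 10. Baseline does not differ by arm in expectation, so

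arm coefficient = effect at week 14 − b6 × effect at week 6 − b10 × effect at week 10.

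- Exchangeable: b6 = b10 = ρ/(1 + 2ρ) = 0.5/2 = 0.250 at ρ = 0.5, and 0.7/2.4 = 0.292 at ρ = 0.7.
  - Constant: 2 − 4 × 0.250 = 1.00; 2 − 4 × 0.292 = 0.83.
  - Building: 2 − 2.5 × 0.250 = 1.38; 2 − 2.5 × 0.292 = 1.27.
- AR(1): b6 = 0 and b10 = ρ.
  - Constant: 2 − 2ρ = 1.00 to 0.60.
  - Building: 2 − 1.5ρ = 1.25 to 0.95.
- Week 14 only: 2.0 in every case.

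**Response reading without arm-by-visit, estimate.** The visit weights are 1/3 each with an exchangeable working correlation. With AR(1) they are proportional to 1, 1 − ρ, 1: 0.40, 0.20, 0.40 at ρ = 0.5, and 0.435, 0.13, 0.435 at ρ = 0.7.

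- Constant: 2.0.
- Building: 1.5 under either structure.
- Week 14 only: 2/3 = 0.67 exchangeable; 2 × 0.40 = 0.80 to 2 × 0.435 = 0.87 AR(1).

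| Effect at weeks 6, 10, 14 | Covariate reading | Response reading, no arm-by-visit | True week-14 effect |
|---|---|---|---|
| 2, 2, 2 | 0.60–1.00 | 2.0 | 2 |
| 1, 1.5, 2 | 0.95–1.38 | 1.5 | 2 |
| 0, 0, 2 | 2.0 | 0.67–0.87 | 2 |

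No row gives 2 on both readings. Fitted GEE models (200 simulated trials per course, exchangeable ρ = 0.6, SD 3.5) agree. For constant, building and week-14-only effects, the covariate model averaged 0.91, 1.33 and 2.02. The model without arm-by-visit averaged 1.98, 1.50 and 0.70. The week-14 contrast from the model with arm-by-visit averaged 1.98, 2.01 and 2.04.

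**Power on the covariate reading, one case in full (constant effect, exchangeable ρ = 0.5, SD 3.5).**

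1. Residual SD = 3.5 × √(1 − 3 × 0.250 × 0.5) = 3.5 × √0.625 = 2.77.
2. Weeks 6 and 10 given baseline have variance 12.25 × 0.75 = 9.19 and covariance 12.25 × 0.25 = 3.06. Arm is correlated with them, so its variance is inflated by 1 + ¼ × 8/(9.19 + 3.06) = 1.163.
3. SE = 2.77 × √(2/135) × √1.163 = 0.363.
4. Power = Φ(1.00/0.363 − 1.96) = Φ(0.79) = 79%.

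**Power and disagreement across scenarios.** Simulated normal data, 135 per arm, t-tests from ordinary regression. Disagreement means that the unadjusted test is significant and the covariate-adjusted test is not.

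| Effect course | SD | Unadjusted power | Covariate-reading power | Disagreement |
|---|---|---|---|---|
| Constant | 3.5 | over 99% | 44–81% | 19–56% |
| Constant | 6 | about 78% | about 20–40% | about 40–60% |
| Building | 3.5 | over 99% | 86% to over 99% | about 0.5–15% |
| Building | 6 | about 78% | not tabulated | 11–36% |
| Week 14 only | 3.5 and 6 | as above | no loss | under 2% |

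**The case against.** The strongest reply is that the plan can be understood as it stands. The unpaired week-14 comparison is the method first attached to the primary outcome, the adjusted analysis comes after it, and the two-group power simulation ("would give us a power of 80% to detect the clinically important difference of 2") mentions neither covariates nor repeated visits. On that view the unadjusted test decides and GEE is supportive. The covariate reading is also the less coherent one: it leaves one response per participant, so GEE would have no repeated response to handle, whereas the plan chose it for repeated measures. The large figures need that reading and a full effect already present at week 6, and the lowest powers also need SD 6 instead of the planned 3.5. Nor does the plan rule out an arm-by-visit term.

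Much of this stands. The unadjusted comparison is sound on either reading, the response reading may well be what was meant, and the harm ranges from none to large on inputs nobody has. But both the order of analyses and the intended model have to be inferred; no sentence states them. The literal wording puts post-treatment scores among the adjusters, and the response reading still lacks the contrast that answers the week-14 question. A simpler remedy, week-14 CVS-Q adjusted for baseline CVS-Q, age and gender, would also be acceptable.

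**Conclusion.** The concern holds and should be fixed; it does not invalidate the trial. That the model and the decisive analysis are not fixed is certain from the text. The numerical consequence is conditional on ρ of 0.5 to 0.7, normal data and an assumed time course. For a true 2-point week-14 effect, the literal model gives 0.60 to 1.00 if the effect is constant, 0.95 to 1.38 if it builds, and 2.0 if it appears only at week 14. The repeated-response model without arm-by-visit gives 2.0, 1.5 and 0.67 to 0.87 respectively. With a sustained effect, the two listed analyses would split at the 0.05 threshold in roughly a fifth to just over half of trials at SD 3.5.

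**What to change.** Rewrite the adjusted analysis so that CVS-Q at weeks 6, 10 and 14 are the responses in the GEE; arm, visit and arm-by-visit are factors; and baseline CVS-Q, age and gender are the only covariates. Weeks 6 and 10 should no longer appear in the adjustment list. State the working correlation, and report the week-14 arm contrast with a robust standard error and 95% confidence interval.

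Add a sentence, fixed before unblinding, saying whether this contrast or the unadjusted week-14 comparison is the primary analysis, with the other supportive. If the unadjusted comparison is chosen, name its test. Weeks 6 and 10 can still be used in the multiple-imputation model.

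The cost is about two sentences of analysis text. The data, visits and software procedure are unchanged.
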